5.3 Primary Study Endpoint

Tumor regression rate of MSS/pMMR patients (Pathological response, percentage of TRG2-4 to all MSS patients, Dworak criteria)

TRG Dworak criteria: Grade 0: no regression; Grade 1: dominant tumor mass with obvious

fibrosis and/or vasculopathy; Grade 2: dominantly fibrotic changes with few tumor cells or groups (easy to find); Grade 3: very few (difficult to find microscopically) tumor cells in fibrotic tissue with or without mucous substance; Grade 4: no tumor cells, only fibrotic mass (total regression or response).

5.4 Secondary Study Endpoint

The secondary endpoints included the tumor pathological downstage rate, defined as the percentage of patients with a lower postoperative stage than baseline stage, pCR rate, R0 resection rate, 2-year DFS, 2-year EFS and OS for MSS/pMMR colon cancer. The pathological response rate and pCR rate for MSI-H/dMMR patients. Perioperative complication rate, mortality and Adverse events (National Cancer Institute Common Terminology Criteria for Adverse Events [NCI CTCAE], version 5.0).

6. Safety Evaluation

6.1 Safety Measurements

6.1.1 Vital Signs

Body temperature, blood pressure, pulse and respirations will be performed after resting for 5 minutes at Screening and every subsequent clinic visit.

6.1.2 Performance Status

The Eastern Cooperative Oncology Group (ECOG) performance status scale will be used (Appendix 3) and will be assessed at Screening and every subsequent clinic visit.

6.1.3 Laboratory Measurements

Blood and urine will be obtained at the time points described in the Schedule of Activities and sent to a central lab for hematology, blood chemistry profile, and urinalysis, respectively. After enrollment, blood routine, liver function and renal function were reviewed weekly, and blood routine, biochemistry, thyroid function, myocardial enzyme profile, troponin and cytokine were reviewed every treatment cycle.

6.1.4 Electrocardiogram (ECG)

A standard 12-lead ECG (with a 10-second rhythm strip) will be collected at Screening and as clinically indicated. ECG results were recorded during the screening period, before each cycle of chemotherapy and before surgical treatment.

6.2 Adverse Events

6.2.1 Chemotherapy-related Adverse Events

1) Oxaliplatin

The most common adverse events observed during the combination of oxaliplatin and 5-fluorouracil/folin were gastrointestinal (diarrhea, nausea, vomiting, and mucositis), hematological (neutropenia, thrombocytopenia), and neurological reactions (acute, dose accumulation, peripheral sensory neuropathy).

2) fluorouracil

Nausea, loss of appetite or vomiting; oral mucositis or ulcers, abdominal discomfort or diarrhea;

Leukopenia is common, most of them reach the lowest point within 2-3 weeks after the start of treatment, and return to normal within 3-4 weeks. Thrombocytopenia. Rarely cough, shortness of breath, or cerebellar ataxia; Hair loss or intravenous hyperpigmentation with drug injection; Extravasation at the intravenous drip may cause local pain, necrosis, or cellulitis. Long-term application can cause neurological toxicity. Occasionally, myocardial ischemia.

6.2.2 Camrelizumab-related Adverse Events

Adverse reactions with an incidence of > 10% included reactive cutaneous capillary endothelial proliferation, anemia, fever, weakness, hypothyroidism, proteinuria, cough, and decreased appetite. Incidence > 1% included: hyponatremia, pulmonary infection, elevated aspartate aminotransferase, elevated γ -glutamyltransferase, elevated blood bilirubin, elevated bound bilirubin, abnormal liver function, neutropenia, decreased white blood cell count, thrombocytopenia, decreased lymphocyte count, hypokalemia, elevated propionate aminotransferase, and lipase increased.

6.2.2.1 Suggestions for symptomatic management of common adverse reactions

The toxicity of immune checkpoint inhibitors (ICPi) is different from other types of antineoplastic drugs, and its severity and duration have their particularity. It can be divided into infusion reactions and immune-related adverse events (irAE). Camrelizumab belongs to this class of drugs, so it is necessary to identify and treat adverse events caused by camrelizumab early to reduce the occurrence of serious toxic events.

Immune-related adverse events are defined as specific events (including pneumonitis, diarrhea/colitis, hepatitis, nephritis/renal dysfunction, rash, and endocrine lesions) for which the subject requires treatment with an immunosuppressive drug.

6.2.2.2 Safety management rules

Safety management rules and relevant guidelines (e.g., ESMO Clinical practice guidelines for the diagnosis, treatment, and follow-up of immunotherapy) for similar products on the market abroad can be referred to assist investigators in the evaluation and management of adverse events in the following systems: gastrointestinal, renal, pulmonary, hepatic, endocrine, cutaneous, and neurological.

The general principle is to first make a differential diagnosis according to standard medical practice, then consider a noninflammatory cause and manage it appropriately. After excluding other causes (e.g., disease progression, infection, or other medications), immune-related adverse events were considered and immunosuppressive agents were used. Testing for autoantibodies is often helpful, and the role of tissue biopsies in diagnosing immune-related adverse events is unclear. Consultation with a medical or surgical specialist is recommended, especially before invasive diagnostic or therapeutic procedures are performed.

Corticosteroids are the mainstay of treatment. Subjects with low grade toxicity who are ambulatory may be considered for the oral equivalent of the recommended intravenous dose. The lower bioavailability of oral corticosteroids should be taken into account when changing to an equivalent dose of oral corticosteroids.

6.2.2.3 infusion reaction

Camrelizumab is a fully human monoclonal antibody, which is less likely to cause infusion reactions and generally does not require prophylactic medication before infusion.

Once the infusion reaction occurs, the infusion should be slowed down or interrupted according to the situation, and clinical supportive treatment should be given, and preventive medication should be given before future medication.

Acute infusion reactions usually develop associated symptoms and signs at the time of or shortly after drug infusion and usually resolve within 24 hours after completion of the infusion. Signs and symptoms include: Anaphylaxis/hypersensitivity (including drug-induced fever), cough, chills, chills/chills, dizziness, headache, fatigue (fatigue, lethargy), rash, itchy/itchy skin, joint pain, muscle pain, low or high blood pressure, nausea, vomiting, sweating (sweating), tachycardia, urticaria (wheals), dyspnea (shortness of breath), or bronchospasm.

All grade 3-4 infusion reactions were reported according to the SAE if they met the SAE criteria. Management of anaphylaxis should be based on institutional medical practice and guidelines. Management of delayed anaphylaxis (e.g., pruritus that develops more than 1 week after the end of the infusion) should be managed with symptomatic treatment (e.g., oral antihistamines or corticosteroids).

6.2.2.4 Grading criteria and treatment recommendations for reactive cutaneous capillary endothelial proliferation (RCCEP)

Table1 Grading criteria and treatment recommendations for RCCEP

Grade	Clinical manifestation	Recommendations
Grade 1	Multiple or single nodules, maximum diameter $\leq 10\text{mm}$, with or without ulceration and hemorrhage	Study drug was continued, and topical treatment was strengthened for those with ulceration and bleeding to prevent infection
Grade 2	Multiple or single nodules, $>10\text{mm}$ in diameter, with or without ulceration	Study drug should be continued, observation or local treatment measures should be taken, such as laser or surgical resection, and topical treatment should be strengthened for those with ulceration and bleeding to prevent infection
Grade 3	Multiple nodules were found throughout the body and complicated by skin infection	Study drug should be held until the severity of the toxicity decreases to Grade 1 or returns to baseline. Observation or topical treatment measures such as laser or surgical resection were taken, and anti-infection treatment should be given to concurrent infection

Grade 4 life-threatening and grade 5 deaths have not yet occurred and are therefore not specified

6.2.3 Apatinib-related Adverse Events

Elevated blood pressure: Most patients with elevated blood pressure occur about 2 weeks after taking medicine, and most patients can generally be well controlled by combined use of antihypertensive drugs.

Proteinuria: Proteinuria generally occurs about 3 weeks after administration of the drug and can be relieved by dose interruption or dose reduction.

Hand-foot syndrome: Hand-foot syndrome usually occurs about 3 weeks after taking medicine, and can be alleviated by symptomatic treatment.

Bleeding: The observed bleeding symptoms included gastrointestinal bleeding, hematemesis, hemoptysis, positive fecal occult blood, positive urinary occult blood, skin bleeding spots, and

rupture of liver metastases. Patients in whom fecal occult blood developed generally developed within the first cycle after taking the drug.

Cardiotoxicity: electrocardiographic abnormalities, including sinus bradycardia, partial ST-T changes, slowing heart rate, QT prolongation, and acute myocardial infarction.

Liver toxicity: transaminase, bilirubin, alkaline phosphatase, lactate dehydrogenase increased, liver enzyme abnormalities mostly occurred at the initial of the second cycle.

6.3 Dose Modifications

6.3.1 Recommendations for Chemotherapy Dose Modifications

During the treatment, the patient's blood routine was monitored. After the first occurrence of grade III-IV neutropenia, the use of G-CSF was recommended after active treatment. In cases of grade IV neutropenia, grade III neutropenia with fever ($>38.5^{\circ}\text{C}$) despite prophylactic colony-stimulating factor treatment, or grade III or higher thrombocytopenia and increased creatinine during treatment that could not be tolerated after treatment, each dose reduction of oxaliplatin and fluorouracil was allowed at the discretion of the investigator if toxicity occurred. There were two levels of dose adjustment. If a reduction of more than two dose levels was required, treatment was discontinued.

Table 2 Dose modifications of oxaliplatin and fluorouracil: hematologic toxicity, nonhematologic toxicity

Dose Level		Drug	Dose
0	-	Oxaliplatin	85mg/m ²
		Fluorouracil	400 mg/m ² (intravenous infusion), 2400 mg/m ² (continuous infusion)
-1	Grade III and IV hematologic toxicity, non-hematologic toxicity (excluding peripheral neurotoxicity)	Oxaliplatin	75mg/m ²
		Fluorouracil	0 mg/m ² (intravenous infusion), 1900 mg/m ² (continuous infusion)
-2	Grade IV hematologic toxicity after 1 dose level reduction of oxaliplatin or fluorouracil	Oxaliplatin	55mg/m ²
		Fluorouracil	0 mg/m ² (intravenous infusion), 1400 mg/m ² (continuous infusion)

Peripheral neurotoxicity: As far as possible, the neurological examination of the subjects was performed by the same investigator, before each cycle of treatment, and the subjects should be reviewed regularly if they develop symptoms or signs of peripheral neurological disease. The administration dose was adjusted according to Table 3

Table 3 Oxaliplatin dose adjustment: Peripheral neurotoxicity

AE	Peripheral neurotoxicity		
	time of duration		
	≤7 days	8-13 days	≥14 days
Hypoesthesia	No change	No change	No change
Hypoesthesia without cold pain	No change	No change	After recovery, the dose was reduced 1 dose
Hypoesthesia with cold pain	No change	1 dose reduction	2 dose reduction
Hypoesthesia with functional impairment	1 dose reduction	2 dose reduction	Discontinued oxaliplatin

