7.6 Pregnancy

If a female subject becomes pregnant during the study, the subject shall immediately terminate the use of the experimental drug and be discharged from the group; if a male subject's partner becomes pregnant during the clinical study, the subject shall continue the clinical study.

8 End of Treatment

A patient may be discontinued from study treatment at any time if the patient, the investigator, feels that it is not in the patient's best interest to continue on study. If a patient's study treatment must be discontinued, this will not result in automatic withdrawal of the patient from the study.

The following is a list of possible reasons for early discontinuation of study treatment:

Disease progression (patients should be highly encouraged to stay on study treatment until there is confirmed radiographic progression)

Any episode of seizure

Any other adverse event that cannot be adequately managed with dose modifications, including dose interruption for ≥ 28 days may require study drug discontinuation, which must be discussed with the Sponsor.

Protocol violation requiring discontinuation of study treatment

Patient is not compliant with study procedures

Lost to follow-up

Patient withdrawal of consent

9 Protocol Violations

A protocol violation occurs when the patient or Investigator fails to adhere to significant protocol requirements affecting the inclusion, exclusion, patient safety and primary endpoint criteria. Protocol violations for this study include, but are not limited to, the following:

- Failure to meet inclusion/exclusion criteria [no waivers will be granted to meet the eligibility criteria]
- Use of a prohibited concomitant medication
- Dose modifications that are not within the protocol specifications
- Any other deviation that presents significant risk or safety concerns to the patient

Failure to comply with Good Clinical Practice (GCP) guidelines will also result in a protocol violation. The Sponsor, in consultation with the Investigator, will determine if a protocol violation should result in withdrawal of a patient.

10 Statistic Method

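### Table 3's row labels overlap with no rule on which row governs, so a patient with hypoesthesia and no cold pain for 14 days or more gets two conflicting oxaliplatin instructions

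*Protocol*

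**What the plan says.** Protocol section 6.3.1 handles peripheral neurotoxicity apart from other toxicities. The level -1 entry in Table 2 excludes it, and the text before Table 3 states: "The administration dose was adjusted according to Table 3". Table 3 is titled "Oxaliplatin dose adjustment: Peripheral neurotoxicity". It crosses four symptom rows with three durations: up to 7 days, 8 to 13 days, and 14 days or more.

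- Row 1 has no qualifier and reads across: "Hypoesthesia No change No change No change".
- Row 2 is labelled "Hypoesthesia without cold pain". It leaves the dose alone in the first two columns. Its last cell reads "After recovery, the dose was reduced 1 dose".
- Row 3 is labelled "Hypoesthesia with cold pain". It moves from no change to one reduction and then two.
- Row 4 covers hypoesthesia with functional impairment. It moves from one reduction to two, and its last cell reads "Discontinued oxaliplatin".

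The protocol does not define row 1 as a separate or milder category and gives no order of precedence among the rows. The SAP does not address dose modification. Under protocol section 3.1 only MSS/pMMR patients receive oxaliplatin, in 5 cycles before surgery and 7 after.

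**The concern.** A dose table works only if each patient at each visit falls in one cell. Here the label of row 1 contains that of row 2, and their last cells differ. Two investigators could assess the same persistent symptom identically, follow the table faithfully, and give different oxaliplatin doses.

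Table 3 is the only rule the protocol states for this toxicity. Section 6.2.1 lists peripheral sensory neuropathy and dose accumulation among oxaliplatin's neurological reactions, so the case is foreseeable over 12 planned cycles. What is at stake is patient safety and consistent delivery of treatment. The sample size and the primary estimate are not in question.

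**Working it through.** The documents give no figure to reproduce, so the check compares the table's cells. The rows use two features, cold pain and functional impairment, which define four types of patient with hypoesthesia. For each type, the matching rows and their instructions, read literally and in row order, are:

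| Patient type | Rows that fit | Up to 7 days | 8 to 13 days | 14 days or more |
|---|---|---|---|---|
| A: neither feature | 1, 2 | none / none | none / none | none / one level after recovery |
| B: cold pain only | 1, 3 | none / none | none / one | none / two |
| C: impairment only | 1, 2, 4 | none / none / one | none / none / two | none / one after recovery / stop |
| D: both | 1, 3, 4 | none / none / one | none / one / two | none / two / stop |

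(None, one and two are the numbers of reductions; stop means that oxaliplatin is discontinued.)

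**Type A.** The two rows agree in the first two columns and conflict in the third. This is the clearest case, because the patient meets both labels exactly and has no further symptom that points to another row.

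**All types.** The matching rows disagree in 1 + 2 + 3 + 3 = 9 of the 12 combinations of type and duration.

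**Can row 1 be a residual category?** Rows 2 and 3 (without and with cold pain) already cover all hypoesthesia. A residual row 1 would contain no patients.

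**Size in dose terms.** Table 2 lists oxaliplatin at 85, 75 and 55 mg/m² for levels 0, -1 and -2. Table 3 does not say that its one dose is one level of Table 2, so this is an assumption. The section's statement that there are two adjustment levels makes it plausible.

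- From level 0: (85 - 75) / 85 = 10 / 85 = 11.8%.
- From level -1: (75 - 55) / 75 = 20 / 75 = 26.7%.

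Row 2 also makes the reduced dose follow recovery, which implies a wait. Its length is not given.

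**The case against.** The best defence is that Table 3 is an ordered ladder. Its instructions never become milder down the rows or across the columns, so row 1 was probably meant as the mildest category, with the most severe matching row applied. Such a rule would settle every combination above. It is not written anywhere, however, and under it row 1 would never decide a dose. Row 1 may have been meant as a different symptom that was lost in wording, but nothing in the documents supplies that meaning. It can also be said that the section offers only recommendations. The sentence that invokes Table 3 is nevertheless direct, and the investigator-discretion sentence concerns blood counts and creatinine. The trial is single-institution, and the same investigator examines each patient where possible. This may limit inconsistent use but does not say which row to use.

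Four stronger inferences are tempting, and the documents do not support them.

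- *The instructions are opposite.* No change and a reduction after recovery conflict, but neither reverses the other.
- *The last column means that the symptom is still present at the next dose.* Table 3 does not tie duration to the infusion day. With 14-day cycles the next dose falls on day 15. A symptom that begins on day 3 and is present then has lasted 12 days and sits in the middle column. A symptom of 14 days or more may have cleared before a delayed dose.
- *Either action is a protocol violation and decides per-protocol membership.* Section 9 lists "Dose modifications that are not within the protocol specifications", but following a printed row is not clearly outside specification. Section 10.1 removes patients from the per-protocol set only for significant deviations or those with a significant impact on results, and the full analysis set is the main one.
- *The primary endpoint is affected.* Seven of the 12 cycles follow surgery, after the tissue for that endpoint is taken, and no effect from the other five is shown.

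**Conclusion.** The point stands as an internal inconsistency in Table 3. For MSS/pMMR patients with hypoesthesia alone lasting 14 days or more, the governing table gives two incompatible oxaliplatin instructions, and the overlap in labels extends to the cold-pain and functional-impairment rows. The dose difference is about 12% for a patient at level 0, and about 27% at level -1, if one dose means one Table 2 level. How many patients would meet the conflict cannot be derived from the documents. The finding rests on the printed labels; the table text appears intact, with four labelled rows and three filled cells in each. It should be corrected because it bears on patient safety and is cheap to put right.

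**What to change.** The sponsor's clinical team should reconcile the rows of Table 3 so that each patient and duration has one instruction. There are two ways to do this: word all four labels so that they are mutually exclusive, stating the feature that separates row 1 from row 2, or keep the labels and add a sentence saying which row governs when more than one applies. Changing only rows 1 and 2 is not enough. Even if row 1 were removed, types C and D would still fit two disagreeing rows in all three columns, 6 of the 12 combinations. The amendment should also say whether one dose in Table 3 means one level of Table 2. This review does not say which instruction is right.

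The cost is a table correction in a protocol amendment and a memo to site staff, with no extra patients, visits or procedures.

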6.3.2 Recommendations for Modifications of Apatinib

Table 4 Recommendations for modifications of apatinib

AE		Grade	Drug held or not	Drug resumed	modification	permanently discontinued
Apatinib related toxicity	hematologic toxicities	Grade 1/2	No	—	—	—
		Grade 3	Yes (except a decreased lymphocyte count)	until toxicity grade decreases to Grade 2	The first time: the original dose; Second time: 5 days on, 2 days off; Third time: medication on alternate days	Grade 3 or higher hematologic toxicity after two dose modification
		Grade 4	Yes	until the severity of the toxicity decreases to Grade 2	The first time: 5 days on, 2 days off; Second time: medication on alternate days	
	Other nonhematologic toxicities *	Grade 1	No	—	—	—
		Grade 2 (lasting more than 7 days)	Yes	until toxicity grade decreases to Grade 1	Original dose	—
		Grade 3	Yes	until toxicity grade decreases to Grade 1	The first time: 5 days on, 2 days off; Second time: medication on alternate days	Grade 3 or higher nonhematologic toxicity after two dose modification
	hypertension	Grade 3 (after treatment)	Yes	until toxicity grade decreases to Grade 1	The first time: the original dose; Second time: 5 days on, 2 days off; Third time: medication on alternate days	After two adjustments, grade 3 hypertension recurred
		hypertensive crisis	Yes	—	permanently discontinued	permanently discontinued
	Proteinuria (without a significant increase in serum creatinine)	Grade 3	Yes	until toxicity grade decreases to Grade 2	The first time: 5 days on, 2 days off; Second time: medication on alternate days	After two adjustments, grade 3 proteinuria recurred
	hand-foot	Grade 3	Yes	until	The first time: 5	After two

	syndrome			toxicity grade decreases to Grade 1	days on, 2 days off; Second time: medication on alternate days	adjustments, grade 3 hand-foot syndrome recurred
	headache	Grade 2 headache lasting \geq 7 days after symptomatic treatment, or grade 3 headache	Yes	until toxicity grade decreases to Grade 1	The first time: 5 days on, 2 days off; Second time: medication on alternate days	After two adjustments, grade 3 headache recurred

* : In the event of cerebral hemorrhage, \geq grade 2 pulmonary hemorrhage, \geq grade 3 other hemorrhage, arterial thrombosis, leukoencephalopathy syndrome, gastrointestinal perforation, and nephrotic syndrome during the trial, apatinib administration and active symptomatic treatment were terminated, and whether to continue camrelizumab treatment was determined depending on the recovery of toxicity of the subjects

